7.2.3 Secondary Objective

Secondary Objective - To assess the safety of simultaneous administration of COVID-19 vaccine with other routinely recommended vaccines among children and adolescent participants.

1) Tables will be produced that summarize each solicited local and systemic reactogenicity event by maximum classification (none, mild, moderate, and severe), as well as by moderate or severe through days 1-7 following COVID-19 vaccination for dose 1 and dose 2 or a booster dose. These tables will have the number and percentage for each classification and will be broken down by concomitant childhood vaccine status (yes/no) by each site and across all sites. (SOM 1, SOM 2 and SOM 3)

2) Tables will be produced that summarize each unsolicited adverse event by maximum classification (none, mild, moderate, and severe), as well as by moderate or severe through days 1-7 following COVID-19 vaccination for dose 1 and dose 2 or a booster dose. These tables will have the number and percentage for each classification and will be broken down by concomitant childhood vaccine status (yes/no) by each site and across all sites. (SOM 4)

3) Tables will be produced that summarize participants experiencing at least one serious adverse event or one AESI through the 29 days after dose 2 or a booster dose. This table will have the number and percentage for each outcome and will be broken down by concomitant childhood vaccine status (yes/no). (SOM5 and SOM6)

The proportions by concomitant vaccine status (yes/no) for secondary outcomes 1 to 6 will be descriptively assessed using an exact Mantel-Haenszel statistic calculated using the Proc Logistic command in SAS at the two-sided alpha 0.05 level. Further details will

be described in the statistical analysis plan. The analysis for exploratory objectives will be described in the statistical analysis plan.

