1 BACKGROUND

As of September 2022, there have been more than 95 million cases of COVID-19 leading to more than one million deaths in the United States (1). Although COVID-19 infection is generally milder in children than adults, it does cause significant pediatric morbidity and mortality. The American Academy of Pediatrics reports that 15 million children have been infected during the pandemic (2), leading to nearly 9000 cases of multisystem inflammatory syndrome in children (MIS-C) and 1500 deaths. From this perspective, safe and effective pediatric COVID-19 vaccines are needed to curb the pandemic.

In May 2021, the FDA issued an Emergency Use Authorization (EUA) for the Pfizer-BioNTech (Pfizer) mRNA COVID-19 vaccine in children aged 12-15. In the Phase III trial leading to the EUA, 2,260 adolescents 12-15 years old were randomized 1:1 to receive 2 doses of 30 ug of the BNT162b2 vaccine or placebo administered 3 weeks apart (3). Pain at the injection site was the most common local reaction, occurring in 86% of vaccine recipients after dose 1, and was somewhat less common after dose 2 (79%). Fatigue (60%), headache (55%), and chills (28%) were the most common systemic events after dose 1. These were slightly more common after dose 2 (fatigue (66%), headache (65%), and chills (42%).

On October 29, 2021 the FDA issued an EUA for the Pfizer-BioNTech vaccine in children aged 5-11 years old, administered as 2 doses of 10 ug 3 weeks apart. The main safety study randomized children 2:1 to BNT162b2 (N=1518) vaccine or placebo (N=750); children were followed for at least 2 months after dose 2. In general, children had less severe systemic reactions than adolescents and young adults following the age-appropriate dose. The most common systemic reactogenicity events in children aged 5-11 years after were fatigue (33.6-39.4%) and headache (22.4-28%). In children aged 5-11 years fever was infrequent after dose 1 (2.5%) and dose 2 (6.5%). There were no serious adverse events in the pediatric study that were considered related to the BNT162b2 study vaccine. No cases of myocarditis or anaphylaxis occurred in the study (4).

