2 STUDY OBJECTIVES

Primary Objective (PO):

To characterize the safety of authorized and recommended COVID-19 vaccines among children and adolescent participants

Secondary Objective (SO):

To assess the safety of simultaneous administration of COVID-19 vaccine with other routinely recommended vaccines among children and adolescent participants

Exploratory Objectives (EO):

EO 1: To assess adolescent and parent perceptions of the COVID-19 vaccine recommendations and experience with receipt of the vaccine

EO 2: To assess the safety of COVID-19 vaccine stratified by baseline COVID-19 serostatus (positive versus negative) in a subset of child and adolescent participants

EO 3: To assess adverse events of special interest through 6 months after dose 2 of COVID-19 vaccine or a booster dose

EO 4: To assess serious adverse events through 6 months after dose 2 of COVID-19 vaccine or a booster dose

EO 5: To assess immune responses to SARS-CoV-2 antigens after COVID-19 vaccine

Primary Outcome Measures (POM):

POM 1: Proportion of participants with defined local or systemic reactogenicity events (stratified according to severity and in total) on days 1-7 after each dose of COVID-19 vaccine

POM 2: Proportion of participants with at least one severe (Grade 3) solicited local or systemic reactogenicity event on days 1-7 after each dose of COVID-19 vaccine

POM 3: Proportion of participants with at least one moderate-to-severe (Grade 2-3) solicited local or systemic reactogenicity event on days 1-7 after each dose of COVID-19 vaccine

POM 4: Proportion of participants with an unsolicited adverse event on days 1-7 after each dose of COVID-19 vaccine

POM 5: Proportion of participants with an adverse event of special interest through 29 days after dose 2 of COVID-19 vaccine or a booster dose

POM 6: Proportion of participants with at least one serious adverse event occurring through 29 days after dose 2 of COVID-19 vaccine or a booster dose and a description of the serious adverse events

Secondary Outcome Measure (SOM):

SOM: Assessment of primary outcome measures 1-6 in those receiving other routinely recommended vaccines simultaneously with each dose COVID-19 vaccine versus those receiving COVID-19 vaccine alone

Exploratory Outcome Measures (EOM):

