7.2.2 Primary Objective

Primary Objective – To characterize the safety of authorized and recommended COVID-19 vaccines among children and adolescent participants

1) Tables will be produced that summarize each solicited local and systemic reactogenicity event by maximum classification (none, mild, moderate, and severe), as well as by moderate or severe through days 1-7 following COVID-19 vaccination for dose 1 and dose 2 or a booster dose. These tables will have the number and percentage for each classification and will be broken down by each site and across all sites. In addition, the number and percentage of participants with at least one moderate-to-severe local or systemic reactogenicity event will be described, as well as the proportion of participants with at least one severe local or systemic reactogenicity event. (POM 1, POM 2 and POM 3)

2) Tables will be produced that summarize each unsolicited adverse event by maximum classification (none, mild, moderate, and severe), as well as by moderate or severe through days 1-7 following COVID-19 vaccination for dose 1 and dose 2 or a booster dose. These tables will have the number and percentage for each classification and will be broken down by each site and across all sites (POM4).

3) Tables will be produced that summarize participants experiencing at least one serious adverse event or one AESI through the 29 days after dose 2 or a booster dose. This table will have the number and percentage for each outcome. Listings with the clinical narratives will also be provided. (POM5 and POM6)

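### The SOM 5-6 table pools two-dose and one-dose children over unequal windows and splits them by a co-vaccine status not defined by dose, so the contrast can be distorted when there is no true effect

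*Combined protocol and SAP*

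**What the plan says.** The outcomes in Section 2 use two units. POM 1-4 are per dose; POM 4, for example, is the "Proportion of participants with an unsolicited adverse event on days 1-7 after each dose of COVID-19 vaccine". POM 5 and 6 are per child over one window: "Proportion of participants with an adverse event of special interest through 29 days after dose 2 of COVID-19 vaccine or a booster dose" and "Proportion of participants with at least one serious adverse event occurring through 29 days after dose 2 of COVID-19 vaccine or a booster dose". The secondary outcome applies all six to a co-vaccine contrast "in those receiving other routinely recommended vaccines simultaneously with each dose COVID-19 vaccine versus those receiving COVID-19 vaccine alone".

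Section 7.2.3 keeps this split. The tables for SOM 1-4 are laid out for dose 1 and for dose 2 or a booster. The table for SOM 5-6 will "summarize participants experiencing at least one serious adverse event or one AESI through the 29 days after dose 2 or a booster dose", and "This table will have the number and percentage for each outcome and will be broken down by concomitant childhood vaccine status (yes/no"). It has no breakdown by dose. An exact Mantel-Haenszel test at two-sided 0.05 covers outcomes 1 to 6. Its strata are not named, and further detail is left to a separate SAP.

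Section 3.1 enrols vaccine-naive children at dose 1 and children with a completed primary series at a booster. Section 7.2.1 defines one Study Cohort for both. Table 1 collects SAEs and AESIs from the contact after dose 1 onwards.

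**The concern.** A first-dose enrollee is at risk after dose 1, between doses and after dose 2. A booster enrollee is at risk after one dose. If the share of first-dose enrollees differs between the *yes* and *no* columns, the columns differ in doses and days at risk, whatever co-vaccination does. The status definition can itself create that difference, because a child with two doses has two occasions to be co-vaccinated.

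Classification is a second problem. Take a child given another vaccine with dose 1 only, who has hives two days after a dose 2 given alone. Counted as *yes*, the event falls under co-administration that did not occur at that dose. Counted as *no*, the dose 1 co-administration disappears. Read against the each-dose wording of the secondary outcome, the child fits neither column.

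At stake is the SAE and AESI part of the only secondary objective, on a question for which the Background says published data are lacking.

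**Working it through.** The plan states no event rate, sample size or power, so there is no design figure to reproduce.

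**Inputs from the document**
- Dose intervals of 3 weeks ("2 doses of 30 ug of the BNT162b2 vaccine or placebo administered 3 weeks apart") and 4 weeks, both from trials cited in Section 1. The study sets no interval of its own, so these are assumptions here.
- Window end: 29 days after dose 2 or booster.
- Total N: 320.

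**Assumed inputs (not in the document)**
- p, chance of co-vaccination at any one dose, independent between doses: 10-50%.
- s, share of first-dose enrollees: 30-70%.
- No true co-vaccine effect.

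**Step 1, time at risk**
- Two doses: 21 + 29 = 50 days, or 28 + 29 = 57 days.
- Booster: 29 days.
- Ratio: 50/29 = 1.72 to 57/29 = 1.97. By number of doses it is 2.

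Let r be the risk in a two-dose child relative to a one-dose child, from 1.72 to 2. Counting 28 days instead of 29 gives 49/28 = 1.75 to 56/28 = 2.00, which makes no material difference.

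**Step 2, null risk ratio.** If a share a of first-dose enrollees and a share b of booster enrollees fall in a column, its mean relative risk is [s·a·r + (1−s)·b] / [s·a + (1−s)·b]. Worked at p = 0.3, s = 0.5, r = 2:

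- *Yes at any dose.* First-dose share in *yes*: 1 − 0.7² = 0.51. Yes: (0.51 + 0.15)/(0.255 + 0.15) = 1.630. No: (0.49 + 0.35)/(0.245 + 0.35) = 1.412. Ratio 1.15.
- *Yes at both doses, one-of-two children in no.* First-dose share in *yes*: 0.3² = 0.09. Yes: (0.09 + 0.15)/(0.045 + 0.15) = 1.231. No: (0.91 + 0.35)/(0.455 + 0.35) = 1.565. Ratio 0.79.
- *Yes at both doses, one-of-two children excluded.* 1.231/1.412 = 0.87.

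Over the full ranges of p, s and r:

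| Meaning of *yes* | Null risk ratio |
|---|---|
| At any dose | 1.07 to 1.20 |
| At both doses, one-of-two children in *no* | 0.69 to 0.89 |
| At both doses, one-of-two children excluded | 0.71 to 1.00 |

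**Step 3, unequal enrolment mix for any reason.** Assume a 1% risk per dose, so two doses give 1 − 0.99² = 1.99%. With first-dose shares of 60% in *yes* and 20% in *no*, the risks are 0.6 × 1.99% + 0.4 × 1% = 1.594% and 0.2 × 1.99% + 0.8 × 1% = 1.198%, a ratio of 1.33. Reversed, it is 0.75. With equal shares it is 1.00.

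**Step 4, a real effect.** Take a true per-dose risk ratio of 2 and a two-dose child co-vaccinated once. The per-child ratio against a two-dose child never co-vaccinated is (1 − 0.99 × 0.98)/(1 − 0.99²) = 0.0298/0.0199 = 1.50. Tabulated by dose it stays at 2.00, and the null value is 1.00.

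**Step 5, effect on the test.** For an assumed 100 *yes* and 220 *no* with no true effect, Fisher's exact test rejects about 3% of the time at risks of 1.66% and 1.44%, and about 9% at the extreme of 1.99% and 1.00%.

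**The case against.** The strongest reply is that the data hold everything needed. Section 5.3 records the date and time of each vaccine given during the study. Section 5.5 limits allergic-type AESIs to 7 days after a vaccination visit and requires a relatedness assessment of each SAE and AESI. Section 7.2.2 promises narrative listings for POM 5-6. A reader might infer that events cannot be tied to a dose; these provisions show that they can. The gap is in the planned table, not in the data.

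Nor does any sentence say that each child carries one fixed status. The same yes/no phrase is used for SOM 1-4, which are laid out by dose, and the separate SAP may supply the rule. This stands: the table is undefined on this point, and the direction of any distortion cannot be read from the plan. But a single count per child over both doses leaves no place for a dose-specific status. Reading dose 2 or booster as two separate tables would still not place a child co-vaccinated at one of two doses.

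A reader might also infer that one or two misplaced events decide the result. The documents do not support that as a general statement. The test is called descriptive. With two events in 320 children, no allocation reaches 0.05 at a 100/220 split (smallest p = 0.097) or a 160/160 split (0.498); it can at 50/270 (0.024).

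Finally, one might extend the point to POM 5-6 or to the six-month outcomes EOM 3-4. A per-child proportion for "participants experiencing at least one serious adverse event or one AESI through the 29 days after dose 2 or a booster dose" is a legitimate description of the schedule received. The six-month outcomes follow their own definition, and the protocol defers their analysis to the SAP.

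**Conclusion.** The point holds for SOM 5-6, as a contrast that can be distorted rather than one shown to be. The unit, the window and the yes/no split do not match the each-dose definition of the secondary outcome. The null risk ratio is about 1.07-1.20 or about 0.69-1.00, depending on a rule the protocol does not give. These figures rest on the assumed dose intervals, co-vaccination frequency, first-dose share and independence between doses. The distortion is nil if first-dose shares are equal in the two columns or enrolment type is a stratum. With few events expected and a descriptive test, the harm is to interpretation more than to the false-positive rate. The change is still worth making, because it is cheap and co-administration is the sole secondary objective. The separate SAP was not available and may already settle it.

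**What to change.** For SOM 5-6, use three rows: after dose 1 up to dose 2, after dose 2 to Day 29, and after booster to Day 29. Assign each event to the most recent COVID-19 dose, and set co-vaccine status by what was given with that dose. State where the dose 1 row ends for a child who never receives dose 2. Show primary-series and booster children separately before any pooled row, or stratify the exact Mantel-Haenszel test by enrolment type. Stratifying alone removes the null distortion but still needs a rule for the child co-vaccinated at one of two doses. Keep the per-child POM 5-6 proportion, shown separately by enrolment type.

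Only table and SAP wording changes; no new data are needed. The price is smaller cells. A primary-series child can also appear in both dose rows, so those rows should be read separately and not added as if independent.

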7.2.4 Exploratory Objective

Exploratory Objective- To assess immune responses to SARS-CoV-2 antigens after COVID-19 vaccine.

The analysis for exploratory objectives will be detailed in the comprehensive Statistical Analysis Plan. .

7.2.5 Safety Monitoring Plan

An interim safety data review of all SAEs will be performed with the goal of identifying unexpected safety concerns of clinical importance. The interim safety data review will be performed by a panel with relevant expertise who are not investigators on the study. The safety review panel will assess the clinical narratives of SAEs and AESIs for all participants who were vaccinated. Additional data reviews will be generated if the CDC and study investigators determine they are needed. There are no statistical analyses planned for this safety data review.

7.3 Data Management Plan

The novel Vanderbilt-designed resource developed specifically for online collection of research information, the Research Electronic Data Capture (REDCap) platform (<https://projectredcap.org/>), will be used to design study forms, including the reaction forms, and short customized questionnaires to collect information from study subjects. REDCap provides: 1) a streamlined process for rapidly building a database; 2) an intuitive interface for collecting data, with data validation and audit trail; 3) automated export procedures for seamless data downloads to common statistical packages; 4) branching logic, file uploading, and calculated fields; and 5) a quick and easy protocol set-up. This system will be used by Duke for data management. All electronic linkages will fulfill regulations for protection of human subjects and requirements to minimize the risk of breach of confidentiality.

All study-related documents containing protected health information, (e.g., enrollment logs, case report forms, memory aids, and perception surveys) completed by study participants, will be maintained in secure research offices at Duke, Cincinnati, Columbia and Kaiser, which are accessible to research staff only.

The study team will utilize a secure, encrypted, file transfer method for sharing study documents and data with the CDC. No personal identifiers will be included in any shared documents or datasets.

7.3.1 Research Electronic Data Capture (REDCap)

REDCap (<http://project-redcap.org/>) assists with the collection and management of data for diverse clinical and translational research studies. REDCap was designed around the concept of giving research teams an easy method to specify project needs and rapidly develop secure, web-based applications for collection, management and sharing of research data. REDCap accomplishes these key functions through use of a single study

metadata table referenced by presentation-level operational modules. Based on this abstracted programming model, databases are developed in an efficient manner with little resource investment beyond the creation of a single data dictionary. The concept of metadata-driven application development is well established, and the critical factor for successful data collection lies in creating a simple workflow methodology allowing research teams to autonomously develop study-related metadata in an efficient manner. Both products include secure institutional data hosting and include full audit-trails in compliance with Health Insurance Portability and Accountability Act (HIPAA) security requirements. The REDCap Consortium is comprised of 647 active institutions. The REDCap currently supports 68,000 projects with over 89,000 users spanning numerous research focus areas across the consortium. The current project will use this software application for the design of electronic forms to collect information from study participants, to link the baseline data, sample collection date, and laboratory results in an automated database family, to perform data cleaning and data quality assurance efficiently, and to design an analytical dataset for the analysis of the project data.

Data will be entered into the REDCap database by members of the study team from Duke, Cincinnati, Columbia, and Kaiser, using the paper case report forms utilized to record data collected as part of study procedures. Study investigators will be responsible for assuring that all paper records are securely stored according to the requirements of their IRBs. The study investigators will be responsible for assuring the accuracy of the data entered from the paper forms into REDCap.

In order to perform data cleaning and data quality assurance efficiently, numerous built-in filters and checks for consistency of the data including range and limit checks, branching logic and pull down menus to limit choices for categorical variables to a pre-specified list will be implemented and performed automatically to minimize data entry error. The data will be randomly sampled and checked against source records on a regular basis. The data and related analytical datasets will also be stored at the lead and contributing sites with secured password-protected computers.

7.3.2 Role of the CDC Investigators in the Project

This study is funded by a CDC contract with Duke University, Cincinnati Children's Hospital, Columbia University, and Kaiser Permanente as Task Orders in the CISA Project Contract. The Duke University PI (will oversee the study in partnership with the Cincinnati Children's Hospital PI, the Columbia University PI and the Kaiser Permanente PI). CDC staff will collaborate with all sites to develop the protocol, conduct the study, ensure the study is aligned with US Department of Health and Human Services (CDC) public health priorities, and analyze the data and disseminate the results. CDC may receive access to coded data not containing any directly identifying information.

8 HUMAN SUBJECTS

8.1 Human Participants Involvement, Characteristics, and Design

Duke, Cincinnati, Columbia, and Kaiser investigators will be responsible for submitting the protocol, informed consent, memory aids, recruitment materials and any written or verbally conveyed materials specific to this project to their institutional review boards. The CDC, as the funding agency, supports an exception to the sIRB mandate for the participating sites under the provision at 114(b)(2)(ii). CDC staff will be responsible for submitting materials to the CDC for review and obtain reliance on Duke IRB.

To facilitate participant recruitment at the practices, we will request a waiver of consent and HIPAA authorization as per institutional requirements for ascertainment (identification, selection) and/or recruitment of potential participants while recording identifiable private health information (PHI) prior to obtaining the participant's consent. This information will be obtained from review of the electronic scheduling and medical record systems in the clinics in order to determine eligibility for study enrollment. The PHI collected prior to consent will be used to recruit and screen only. Use of PHI in this manner involves no more than minimal risk to participants and no information will leave the study sites. Informed consent will be sought in accordance with 45 CFR 46.116, prior to enrollment.

Continuing reviews will be submitted to the IRBs in accordance with the new Common Rule. Protocol deviations or concerns about study integrity will be reported promptly to the overseeing IRB in accordance with institutional requirements.

